8.3. Stopping Rules and Withdrawal Data Requirements

There are no stopping rules for halting the trial for this study.

If a participant discontinues from the study, the reason given must be recorded in source documentation and the end of study page on the CRF or in the electronic data capture system (EDCS). If the participant is being withdrawn because of an AE, that AE must be indicated as the reason for withdrawal. Participants who discontinue from the study are not replaced.

9. Endpoints and Analyses

9.1. Primary Efficacy

9.1.1. Endpoint

The primary efficacy endpoint for the pilot study is change from baseline in VAS pain score at 3 months.

[figure not shown]
The primary efficacy endpoint for the comparative study is change from baseline in VAS pain score at 12 months.

9.1.2. Analysis

For the pilot study, the VAS pain score and change from baseline value will be summarized with descriptive statistics. The change from baseline will be calculated as

For the comparative study, the VAS pain score and change from baseline value at 12 months will be summarized by treatment group and visit with descriptive statistics. In addition, tests of non-inferiority and superiority of Axoguard Nerve Cap to neurectomy with respect to VAS pain score will be conducted using closed testing procedures.

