All summaries of categorical data will be presented in frequencies and percentages. All summaries of continuous data will be presented by the number of non-missing values, mean, standard deviation, standard error, median, minimum, maximum, and coefficient of variation. Mann-Whitney U tests will be used to compare baseline data to ensure poolability across centers.

Sample Size and Analysis of Data:

The study is a randomized, controlled, prospective, subject blinded, multi-center study to evaluate the safety and performance of Axoguard® Nerve Cap for the treatment of symptomatic neuroma as compared to neurectomy. Tests of non-inferiority and superiority will be conducted in the comparative phase. Sample sizes for both pilot (15 subjects) and comparative (86 subjects) study phases were based on similar injury-type studies published and referenced in the protocol. As a point of reference, outcomes will also be compared to historical controls of subjects undergoing neurectomy.

Table of Contents

1. INTRODUCTION	5
1.1 BACKGROUND	5
1.2 Product Description	6
1.3 RISK ANALYSIS	8
1.3.1 Preclinical Testing for Axoguard® Nerve Cap	8

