3. STUDY DESIGN

3.1 Description of Design

This is a multicenter, prospective, randomized, controlled, subject blinded comparative parallel group study in patients presenting with symptomatic neuroma (verified by diagnostic block or imaging (US or MRI confirmation) with a baseline pain level of \geq 65 mm on a 100 mm Visual Analog Scale (VAS) during screening. Fifteen (15) pilot subjects will receive the Axoguard® Nerve Cap in the pilot phase of the study. In the comparative phase of the study, approximately 86 adult subjects meeting inclusion/exclusion criteria will be centrally randomized in a 1:1 ratio to receive either Axoguard® Nerve Cap or neurectomy. This study design overview is found in Figure 3.1. This study is intended to collect post-operative data as well as physician experience surveys on the clinical use of Axoguard® Nerve Cap to evaluate its safety and performance as compared to subjects receiving neurectomy.

Figure 3.1. Study Design

This study will consist of a total of 8 visits

This study will be conducted in

accordance with the FDA regulations21 CFR Parts 50 and 56 and current cGCP requirements as described in the ISO 14155:2011 standards, applicable IRB regulations.

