5. STATISTICAL CONSIDERATIONS

Descriptive statistical methods will be used to summarize the data from this study. Unless stated otherwise, the term "descriptive statistics" refers to number of events (n), mean, median, standard deviation (SD), standard error, minimum, maximum, and coefficient of variation (CV) for continuous data and frequencies and percentages for categorical data. All data collected during the study will be included in data listings. Unless otherwise noted, the data will be sorted by subject number, and then by date within each subject number.

Unless specified otherwise, all statistical testing will be two-sided and will be performed using an overall significance (alpha) level of 0.05.

All statistical analyses will be conducted with the SAS® System, version 9.1.3 or higher.

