5.7.2 Covariates

These analyses may be stratified to identify other important factors which may impact nerve recovery such as ag

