5.7.3 Planned Subgroups

5.7.4 Missing Data

Every effort will be made to obtain the required data at each scheduled evaluation from all subjects who have been randomized. In assessing the primary efficacy endpoint, a repeated measures mixed model will be utilized on all observed data.

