7.1. Sample Size and Power

A total of 101 participants (15 pilot; 86 comparative/randomized) at up to 20 sites will be enrolled.

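### The primary Month 12 VAS comparison shows no baseline VAS term; adding one is nearly free and makes the loose endpoint wording harmless

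*SAP*

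**What the plan says.** **Endpoint.** SAP 9.1.1: "The primary efficacy endpoint for the comparative study is change from baseline in VAS pain score at 12 months". SAP 4 describes it as a between-group difference in change. Protocol 5.5.1 refers to the mean VAS change, and Protocol 5.10 defines success by the reduction in VAS. (Protocol 5.8.1 gives 3 months for both phases. That is a separate discrepancy and does not affect this point.)

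**Objective and test.** SAP 3.1 states the comparative objective as a difference in VAS pain scores at 12 months. SAP 9.1.2 says that non-inferiority and "superiority of Axoguard Nerve Cap to neurectomy with respect to VAS pain score will be conducted using closed testing procedures". The test paragraph of Protocol 5.2 is worded similarly. SAP 9.1.2 names no test, model or covariate, whereas SAP 9.2.1 names a test for each secondary endpoint.

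**Model.** Protocol 5.7.4 says that for the primary efficacy endpoint "a repeated measures mixed model will be utilized on all observed data". It lists no model terms, and SAP 9.1.2 does not repeat the model.

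**Covariates.** Protocol 5.7.2 is optional and exploratory: "These analyses may be stratified to identify other important factors". The rest of that sentence is cut off.

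**Baseline data.** Protocol 3.9.1 and 3.9.2 and the Schedule of Assessments collect VAS before the nerve block, at screening or on the operative day. SAP 6 allows baseline to be Day 0 or the screening period, depending on the analysis.

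**The concern.** Every randomised subject should have a pre-operative VAS, yet no visible text uses it in the primary comparison except as the value subtracted to form the change.

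Subtracting baseline fixes the baseline slope at 1. Ignoring baseline, as a test on the Month 12 score would, fixes it at 0. A model with baseline as a covariate estimates the slope, so in large samples it is at least as precise as either. It also corrects for a chance difference in baseline between the arms.

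Two things are at stake: some precision in a trial of 86 subjects, and having a single primary estimate that does not depend on how the words VAS pain score are read.

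**Working it through.** **1. The plan's own figure.** "approximately 86 adult subjects meeting inclusion/exclusion criteria will be centrally randomized in a 1:1 ratio" (Protocol 3.1), so 43 per arm. "all statistical testing will be two-sided and will be performed using an overall significance (alpha) level of 0.05" (Protocol 5). SAP 7.1 says only "A total of 101 participants (15 pilot; 86 comparative/randomized) at up to 20 sites will be enrolled". The protocol synopsis says the sizes "were based on similar injury-type studies published and referenced in the protocol". No power, effect, SD, margin or dropout is visible, so 86 cannot be reproduced. Back-solving for 80% power gives difference/SD = (1.960 + 0.842) × √(2/43) = 0.604. That is an SD of 23.2 mm for a 14 mm difference and 33.1 mm for 20 mm. The 14-20 mm range is the clinically significant difference in Protocol 1.1.

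**2. Assumptions.** None of these is in the documents.
- Month 12 SD s1 = 25 or 30 mm, which lies inside the back-solved range.
- Baseline SD s0 = 8 or 10.1 mm. Entry at about 65 mm on a 100 mm scale narrows the baseline; a uniform spread over 65-100 gives 35/√12 = 10.1.
- Baseline-to-Month-12 correlation r = 0 to 0.4.
- No dropout.

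**3. Formulas.**
- Variance of change: s0² + s1² − 2·r·s0·s1
- Variance of Month 12 score: s1²
- Baseline-adjusted variance V: s1²·(1 − r²)
- Power for difference d (normal approximation): Φ(d/√(2V/43) − 1.96), with the relevant variance as V

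**4. Variance of change → adjusted variance (saving).**

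| s1, s0 | r = 0 | r = 0.2 | r = 0.3 | r = 0.4 |
|---|---|---|---|---|
| 25, 8 | 689 → 625 (9.3%) | 609 → 600 (1.5%) | 569 → 569 (0.0%) | 529 → 525 (0.8%) |
| 25, 10.1 | 727 → 625 (14.0%) | 626 → 600 (4.2%) | 575.5 → 568.8 (1.2%) | 525 → 525 (0.0%) |
| 30, 8 | 964 → 900 (6.6%) | 868 → 864 (0.5%) | 820 → 819 (0.1%) | 772 → 756 (2.1%) |
| 30, 10.1 | 1002 → 900 (10.2%) | 881 → 864 (1.9%) | 820 → 819 (0.1%) | 759.6 → 756 (0.5%) |

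Against the raw Month 12 score the saving is r²: 0%, 4%, 9% and 16%.

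**5. Power for an assumed 15 mm difference, change v adjusted.**
- r = 0, largest gain (s1 = 25, s0 = 10.1): 15/√(2 × 727/43) − 1.96 = 0.62, power 73.2%; with 625 it is 0.82, power 79.4%. Gain 6.2 points.
- r = 0, smallest gain (s1 = 30, s0 = 8): 61.0% v 64.0%. Gain 3.0 points.
- r = 0.2: gain 0.2 to 1.6 points.
- r = 0.3 to 0.4: gain 0 to 0.9 points.

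**6. Finite samples.** In a 40,000-replicate simulation (s0 = 10, s1 = 25, r = 0.3, difference 14 mm, 43 per arm), power was 76.4% for a t-test on change and 76.1% for ANCOVA. Where the true slope is close to 1, estimating it gains nothing.

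**7. Score and change coincide once baseline is in the model.** If score = a + τ·arm + β·baseline, then change = a + τ·arm + (β − 1)·baseline. The treatment effect τ, its standard error and its interval are identical. The same holds visit by visit in the repeated measures model.

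**The case against.** **The endpoint is already settled as change.** This stands. A reader might infer that the sponsor is free to choose between a test on score and a test on change. In simulation (s0 = 10, s1 = 25 or 30, r = 0.2-0.3, true difference 14 mm) two such unadjusted t-tests disagree at 0.05 in about 11% of trials. With no true difference (s1 = 25, r = 0.2), taking whichever is significant raises type I error to 6.9%. The documents do not support that reading. SAP 4 and 9.1.1 and Protocol 5.5.1 and 5.10 all say change or reduction, and VAS pain score in the test sentence most naturally names the instrument. The protocol also specifies a repeated measures mixed model, not a pair of simple tests.

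**An unadjusted comparison of change is valid.** This stands too. Randomisation protects it, and its standard error already reflects chance imbalance.

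**The relevant text may be hidden.** This stands in part. Protocol 5.7.2 breaks off, the Hypotheses Tested section listed in the contents is not visible, and a formula is missing from SAP 9.1.2. A baseline term, or a mixed model with baseline as a response, cannot be excluded. But what is visible in 5.7.2 is optional, the missing formula belongs to the pilot phase, and the comparative test sentence is complete.

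**The gain may be negligible.** This is true at r = 0.3-0.4 against change. The largest savings against change (r = 0) and against the raw score (r = 0.4) cannot occur together.

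**Conclusion.** The point holds as an inexpensive improvement, not as an error that invalidates the analysis. No visible text in SAP 9.1.2 or Protocol 5.7.4 puts baseline VAS into the primary comparison.

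Against the defined endpoint, change, adjustment saves 7-14% of variance if baseline and Month 12 VAS are uncorrelated (3-6 power points at 15 mm), 0.5-4% at correlation 0.2, and about 0-2% at 0.3-0.4. Against the raw score it would save 0-16%. All of this rests on assumed SDs and correlations and on 43 per arm with no dropout.

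Two stronger conclusions might be inferred and are not supported: that precision is certainly lost, since the saving can be nil, and that the sample size of 86 is wrong, since its basis is not visible. What remains even at zero gain is that a baseline term makes the loose wording in SAP 3.1 and 9.1.2 harmless.

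**What to change.** In SAP 9.1.2, with matching text in Protocol 5.7.4, state that:
- the Month 12 treatment contrast comes from the protocol's repeated measures mixed model with pre-nerve-block baseline VAS and baseline-by-visit terms, or from ANCOVA on baseline if only Month 12 is analysed;
- that one estimate and its 95% CI are used for both the non-inferiority and the superiority step;
- unadjusted change is reported descriptively.

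Naming the pre-nerve-block value also settles which baseline the primary analysis uses, which SAP 6 leaves open. While editing, reconcile the model on all observed data in Protocol 5.7.4 with SAP 7.3, which says that missing primary data will be imputed.

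Cost: one sentence in each document and no new data. ANCOVA uses one degree of freedom. Baseline-by-visit uses one per post-operative visit modelled, so at most six.

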9.2. Secondary Efficacy

9.2.1. Endpoints and Analyses

For the comparative study, all secondary endpoints will be summarized by visit with descriptive statistics by treatment group and using a comparative analysis.

	Endpoint	Analysis
1.	The change from baseline of PROMIS Pain Behavior	The treatment groups' scores will be
	Scale score at Month 12	compared with a t-test.
2.	The change from baseline of FHSQ in the General	The treatment groups' scores will be
	Foot Health Scale score at Month 12.	compared with a t-test.
3.	The change from baseline of quantity, quality and	The MME will be compared in the
	class of pain medication use as quantified by MME	treatment groups using a t-test.
	dosing at Month 12.	
4.	The change from baseline of quantity, quality and	The MQS score will be compared in
	class of pain medication use as quantified by the	the treatment groups using a t-test.
	MQS score at Month 12.	
	`	
5.	Recurrence of symptomatic neuroma at Month 12.	Proportion of patients with recurrence
	(Note: Assessments at each visit will be independent.	will be compared between the
	For example, it is possible for a subject to have a	treatment groups using a Fisher's
	recurrence at Month 3 and not have a recurrence at	exact test.
	Month 6.)	

Endpoint	Analysis
6. The Area Under Curve (AUC) of daily pain diary	The AUC will be compared in the
scores and VAS scores during the 12 months	treatment groups using a t-test or other
following the procedure.	appropriate statistical test as
	determined by a biostatistician.

9.3. Safety

9.3.1. Endpoints

The following measures will be collected and assessed for both the pilot and comparative studies.

Primary safety endpoints:

- 1. The rate of occurrence of SAEs at 3 months.
- 2. The rate or occurrence of AEs or UADEs at 3 months.

Secondary Safety Endpoints:

[figure not shown]
The rate of occurrence of SAEs, AEs and/or UADEs at 6, 9 and 12 months.

[figure not shown]
9.3.2. Analyses

All AEs will be summarized by seriousness, relatedness to the treatment (as assessed by the participant's physician) and severity. All AEs will be listed for individual participants.

9.4. Tertiary/Exploratory Efficacy

10. Protocol Deviations

This study is intended to be conducted as described in the protocol. In the event of a significant deviation from the protocol due to an emergency, accident, or mistake, the investigator or designee must contact the sponsor at the earliest possible time by telephone. This will allow an early joint decision regarding the participant's continuation in the study. This decision will be documented by the investigator and the sponsor and reviewed by the monitor. Protocol deviations will be recorded on a deviation log at each site and tracked outside of the study database.

11. References

[figure not shown]
- 1. Healthmeasures.net. (2018). PROMIS. [online] Available at: http://www.healthmeasures.net/explore-measurement-systems/promis [Accessed 3 Oct. 2018].
- 2. FHSQ. (2018). Home. [online] Available at: https://www.fhsq.org/ [Accessed 3 Oct. 2018].

4. Harden, R. Norman, et al. "Medication Quantification Scale Version III: update in medication classes and revised detriment weights by survey of American Pain Society Physicians." *The Journal of Pain* 6.6 (2005): 364-371

12. Reviewed and Approved By

13. Appendix A: List of Tables, Listings, and Figures

14. Appendix B: PROMIS Questionnaire Scoring Conversion Tables

	Physical Function	
Raw Summed Score	T-score	Standard Error of T-Score
6	21.0	3.8
7	25.0	2.7
8	27.1	2.4
9	28.8	2.2
10	30.1	2.1
11	31.3	2.0
12	32.3	2.0
13	33.2	1.9
14	34.2	1.9
15	35.0	1.9
16	35.9	1.9
17	36.8	1.9
18	37.6	1.9
19	38.5	1.9
20	39.3	1.9
21	40.2	1.9
22	41.2	1.9
23	42.1	1.9
24	43.2	2.0
25	44.3	2.0
26	45.6	2.2
27	47.1	2.3
28	48.9	2.7
29	51.3	3.0
30	59.0	6.2

	Pain Intensity	
Raw Summed Score	T-score	Standard Error of T-Score
3	30.7	4.5
4	36.3	3.1
5	40.2	3.0
6	43.5	3.0
7	46.3	3.0
8	49.4	2.9

9	52.1	2.8
10	54.5	2.9
11	57.5	3.1
12	60.5	3.1
13	64.1	3.8
14	67.4	4.2
15	71.8	5.0

	Pain Interference	
Raw Summed Score	T-score	Standard Error of T-Score
8	40.7	5.9
9	47.9	2.4
10	49.9	1.8
11	51.2	1.5
12	52.3	1.4
13	53.2	1.4
14	54.1	1.4
15	55.0	1.4
16	55.8	1.4
17	56.6	1.4
18	58.1	1.3
19	58.1	1.3
20	58.8	1.3
21	59.5	1.3
22	60.2	1.3
23	60.8	1.3
24	61.5	1.3
25	62.1	1.3
26	62.8	1.3
27	63.5	1.3
28	64.1	1.3
29	64.8	1.3
30	65.5	1.3
31	66.2	1.3
32	66.9	1.3
33	67.7	1.3
34	68.4	1.3
35	69.2	1.3

36	70.1	1.4
37	71.0	1.4
38	72.1	1.6
39	73.5	2.0
40	77.0	3.5

	Fatigue	
Raw Summed Score	T-score	Standard Error of T-Score
8	33.1	4.8
9	38.5	2.7
10	41	2.2
11	42.8	2
12	44.3	1.9
13	45.6	1.8
14	46.9	1.8
15	48.1	1.8
16	49.2	1.8
17	50.4	1.8
18	51.5	1.7
19	52.5	1.7
20	53.6	1.7
21	54.6	1.7
22	55.6	1.7
23	56.6	1.7
24	57.5	1.7
25	58.5	1.7
26	59.4	1.7
27	60.4	1.7
28	61.3	1.7
29	62.3	1.7
30	63.3	1.7
31	64.3	1.7
32	65.3	1.7
33	66.4	1.7
34	67.5	1.7
35	68.6	1.7
36	69.8	1.8
37	71	1.8

38	72.4	2
39	74.2	2.4
40	77.8	3.7

Sleep Disturbance		
Raw Summed Score	T-score	Standard Error of T-Score
8	28.9	4.8
9	33.1	3.7
10	35.9	3.3
11	38.0	3.0
12	39.8	2.9
13	41.4	2.8
14	42.9	2.7
15	44.2	2.7
16	45.5	2.6
17	46.7	2.6
18	47.9	2.6
19	49.0	2.6
20	50.1	2.5
21	51.2	2.5
22	52.2	2.5
23	53.3	2.5
24	54.3	2.5
25	55.3	2.5
26	56.3	2.5
27	57.3	2.5
28	58.3	2.5
29	59.4	2.5
30	60.4	2.5
31	61.5	2.5
32	62.6	2.5
33	63.7	2.6
34	64.8	2.6
35	66.1	2.7
36	67.5	2.8
37	69.0	3.0
38	70.8	3.2
39	73.0	3.5

40	76.5	4.4
. 0	, 0.0	** *

20 32.9 0.53 21 38.0 0.38 22 40.6 0.33 23 42.4 0.30 24 43.8 0.27 25 45.0 0.25 26 46.0 0.23 27 46.9 0.21 28 47.7 0.20 29 48.4 0.19 30 49.0 0.18 31 49.6 0.18 32 50.2 0.17 33 50.7 0.16 34 51.2 0.16 35 51.7 0.16 36 52.1 0.15 37 52.6 0.15 38 53.0 0.15 39 53.4 0.15 40 53.8 0.14 41 54.2 0.14 42 54.6 0.14 43 55.0 0.14 45 55.7	Pain Behavior		
21 38.0 0.38 22 40.6 0.33 23 42.4 0.30 24 43.8 0.27 25 45.0 0.25 26 46.0 0.23 27 46.9 0.21 28 47.7 0.20 29 48.4 0.19 30 49.0 0.18 31 49.6 0.18 32 50.2 0.17 33 50.7 0.16 34 51.2 0.16 35 51.7 0.16 36 52.1 0.15 37 52.6 0.15 38 53.0 0.15 39 53.4 0.15 40 53.8 0.14 41 54.2 0.14 42 54.6 0.14 43 55.0 0.14 44 55.3 0.14 45 55.7	Raw Summed Score	T-score	Standard Error of T-Score
22 40.6 0.33 23 42.4 0.30 24 43.8 0.27 25 45.0 0.25 26 46.0 0.23 27 46.9 0.21 28 47.7 0.20 29 48.4 0.19 30 49.0 0.18 31 49.6 0.18 32 50.2 0.17 33 50.7 0.16 34 51.2 0.16 35 51.7 0.16 36 52.1 0.15 37 52.6 0.15 38 53.0 0.15 39 53.4 0.15 40 53.8 0.14 41 54.2 0.14 42 54.6 0.14 43 55.0 0.14 44 55.3 0.14 45 55.7 0.14 46 56.0	20	32.9	0.53
23 42.4 0.30 24 43.8 0.27 25 45.0 0.25 26 46.0 0.23 27 46.9 0.21 28 47.7 0.20 29 48.4 0.19 30 49.0 0.18 31 49.6 0.18 32 50.2 0.17 33 50.7 0.16 34 51.2 0.16 35 51.7 0.16 36 52.1 0.15 37 52.6 0.15 38 53.0 0.15 39 53.4 0.15 40 53.8 0.14 41 54.2 0.14 42 54.6 0.14 43 55.0 0.14 44 55.3 0.14 45 55.7 0.14 46 56.0 0.14 47 56.4 0.14 48 56.7 0.14 49	21	38.0	0.38
24 43.8 0.27 25 45.0 0.25 26 46.0 0.23 27 46.9 0.21 28 47.7 0.20 29 48.4 0.19 30 49.0 0.18 31 49.6 0.18 32 50.2 0.17 33 50.7 0.16 34 51.2 0.16 35 51.7 0.16 36 52.1 0.15 37 52.6 0.15 38 53.0 0.15 39 53.4 0.15 40 53.8 0.14 41 54.2 0.14 42 54.6 0.14 43 55.0 0.14 44 55.3 0.14 45 55.7 0.14 46 56.0 0.14 47 56.4 0.14 48 56.7 0.14 49 57.1 0.14 50	22	40.6	0.33
25 45.0 0.25 26 46.0 0.23 27 46.9 0.21 28 47.7 0.20 29 48.4 0.19 30 49.0 0.18 31 49.6 0.18 32 50.2 0.17 33 50.7 0.16 34 51.2 0.16 35 51.7 0.16 36 52.1 0.15 37 52.6 0.15 38 53.0 0.15 39 53.4 0.15 40 53.8 0.14 41 54.2 0.14 42 54.6 0.14 43 55.0 0.14 44 55.3 0.14 44 55.3 0.14 45 55.7 0.14 46 56.0 0.14 47 56.4 0.14 48 56.7 0.14 49 57.1 0.14 50	23	42.4	0.30
26 46.0 0.23 27 46.9 0.21 28 47.7 0.20 29 48.4 0.19 30 49.0 0.18 31 49.6 0.18 32 50.2 0.17 33 50.7 0.16 34 51.2 0.16 35 51.7 0.16 36 52.1 0.15 37 52.6 0.15 38 53.0 0.15 39 53.4 0.15 40 53.8 0.14 41 54.2 0.14 42 54.6 0.14 43 55.0 0.14 44 55.3 0.14 45 55.7 0.14 46 56.0 0.14 47 56.4 0.14 48 56.7 0.14 49 57.1 0.14 50 57.4 0.14 51 57.8 0.14 52	24	43.8	0.27
27 46.9 0.21 28 47.7 0.20 29 48.4 0.19 30 49.0 0.18 31 49.6 0.18 32 50.2 0.17 33 50.7 0.16 34 51.2 0.16 35 51.7 0.16 36 52.1 0.15 37 52.6 0.15 38 53.0 0.15 39 53.4 0.15 40 53.8 0.14 41 54.2 0.14 42 54.6 0.14 43 55.0 0.14 44 55.3 0.14 44 55.3 0.14 45 55.7 0.14 46 56.0 0.14 47 56.4 0.14 48 56.7 0.14 49 57.1 0.14 50 57.4 0.14 51 57.8 0.14 52	25	45.0	0.25
28 47.7 0.20 29 48.4 0.19 30 49.0 0.18 31 49.6 0.18 32 50.2 0.17 33 50.7 0.16 34 51.2 0.16 35 51.7 0.16 36 52.1 0.15 37 52.6 0.15 38 53.0 0.15 39 53.4 0.15 40 53.8 0.14 41 54.2 0.14 42 54.6 0.14 43 55.0 0.14 44 55.3 0.14 45 55.7 0.14 46 56.0 0.14 47 56.4 0.14 48 56.7 0.14 49 57.1 0.14 50 57.4 0.14 51 57.8 0.14 52 58.1 0.14	26	46.0	0.23
29 48.4 0.19 30 49.0 0.18 31 49.6 0.18 32 50.2 0.17 33 50.7 0.16 34 51.2 0.16 35 51.7 0.16 36 52.1 0.15 37 52.6 0.15 38 53.0 0.15 39 53.4 0.15 40 53.8 0.14 41 54.2 0.14 42 54.6 0.14 43 55.0 0.14 44 55.3 0.14 45 55.7 0.14 46 56.0 0.14 47 56.4 0.14 48 56.7 0.14 49 57.1 0.14 50 57.4 0.14 51 57.8 0.14 52 58.1 0.14	27	46.9	0.21
30 49.0 0.18 31 49.6 0.18 32 50.2 0.17 33 50.7 0.16 34 51.2 0.16 35 51.7 0.16 36 52.1 0.15 37 52.6 0.15 38 53.0 0.15 39 53.4 0.15 40 53.8 0.14 41 54.2 0.14 42 54.6 0.14 43 55.0 0.14 44 55.3 0.14 45 55.7 0.14 46 56.0 0.14 47 56.4 0.14 48 56.7 0.14 49 57.1 0.14 50 57.4 0.14 52 58.1 0.14	28	47.7	0.20
31 49.6 0.18 32 50.2 0.17 33 50.7 0.16 34 51.2 0.16 35 51.7 0.16 36 52.1 0.15 37 52.6 0.15 38 53.0 0.15 39 53.4 0.15 40 53.8 0.14 41 54.2 0.14 42 54.6 0.14 43 55.0 0.14 44 55.3 0.14 45 55.7 0.14 46 56.0 0.14 47 56.4 0.14 48 56.7 0.14 49 57.1 0.14 50 57.4 0.14 51 57.8 0.14 52 58.1 0.14	29	48.4	0.19
32 50.2 0.17 33 50.7 0.16 34 51.2 0.16 35 51.7 0.16 36 52.1 0.15 37 52.6 0.15 38 53.0 0.15 39 53.4 0.15 40 53.8 0.14 41 54.2 0.14 42 54.6 0.14 43 55.0 0.14 44 55.3 0.14 45 55.3 0.14 45 55.7 0.14 46 56.0 0.14 47 56.4 0.14 48 56.7 0.14 49 57.1 0.14 50 57.4 0.14 51 57.8 0.14 52 58.1 0.14	30	49.0	0.18
33 50.7 0.16 34 51.2 0.16 35 51.7 0.16 36 52.1 0.15 37 52.6 0.15 38 53.0 0.15 39 53.4 0.15 40 53.8 0.14 41 54.2 0.14 42 54.6 0.14 43 55.0 0.14 44 55.3 0.14 45 55.7 0.14 46 56.0 0.14 47 56.4 0.14 48 56.7 0.14 49 57.1 0.14 50 57.4 0.14 51 57.8 0.14 52 58.1 0.14	31	49.6	0.18
34 51.2 0.16 35 51.7 0.16 36 52.1 0.15 37 52.6 0.15 38 53.0 0.15 39 53.4 0.15 40 53.8 0.14 41 54.2 0.14 42 54.6 0.14 43 55.0 0.14 44 55.3 0.14 45 55.7 0.14 46 56.0 0.14 47 56.4 0.14 48 56.7 0.14 49 57.1 0.14 50 57.4 0.14 51 57.8 0.14 52 58.1 0.14	32	50.2	0.17
35 51.7 0.16 36 52.1 0.15 37 52.6 0.15 38 53.0 0.15 39 53.4 0.15 40 53.8 0.14 41 54.2 0.14 42 54.6 0.14 43 55.0 0.14 44 55.3 0.14 45 55.7 0.14 46 56.0 0.14 47 56.4 0.14 48 56.7 0.14 49 57.1 0.14 50 57.4 0.14 51 57.8 0.14 52 58.1 0.14	33	50.7	0.16
36 52.1 0.15 37 52.6 0.15 38 53.0 0.15 39 53.4 0.15 40 53.8 0.14 41 54.2 0.14 42 54.6 0.14 43 55.0 0.14 44 55.3 0.14 45 55.7 0.14 46 56.0 0.14 47 56.4 0.14 48 56.7 0.14 49 57.1 0.14 50 57.4 0.14 51 57.8 0.14 52 58.1 0.14	34	51.2	0.16
37 52.6 0.15 38 53.0 0.15 39 53.4 0.15 40 53.8 0.14 41 54.2 0.14 42 54.6 0.14 43 55.0 0.14 44 55.3 0.14 45 55.7 0.14 46 56.0 0.14 47 56.4 0.14 48 56.7 0.14 49 57.1 0.14 50 57.4 0.14 51 57.8 0.14 52 58.1 0.14	35	51.7	0.16
38 53.0 0.15 39 53.4 0.15 40 53.8 0.14 41 54.2 0.14 42 54.6 0.14 43 55.0 0.14 44 55.3 0.14 45 55.7 0.14 46 56.0 0.14 47 56.4 0.14 48 56.7 0.14 49 57.1 0.14 50 57.4 0.14 51 57.8 0.14 52 58.1 0.14	36	52.1	0.15
39 53.4 0.15 40 53.8 0.14 41 54.2 0.14 42 54.6 0.14 43 55.0 0.14 44 55.3 0.14 45 55.7 0.14 46 56.0 0.14 47 56.4 0.14 48 56.7 0.14 49 57.1 0.14 50 57.4 0.14 51 57.8 0.14 52 58.1 0.14	37	52.6	0.15
40 53.8 0.14 41 54.2 0.14 42 54.6 0.14 43 55.0 0.14 44 55.3 0.14 45 55.7 0.14 46 56.0 0.14 47 56.4 0.14 48 56.7 0.14 49 57.1 0.14 50 57.4 0.14 51 57.8 0.14 52 58.1 0.14	38	53.0	0.15
41 54.2 0.14 42 54.6 0.14 43 55.0 0.14 44 55.3 0.14 45 55.7 0.14 46 56.0 0.14 47 56.4 0.14 48 56.7 0.14 49 57.1 0.14 50 57.4 0.14 51 57.8 0.14 52 58.1 0.14	39	53.4	0.15
42 54.6 0.14 43 55.0 0.14 44 55.3 0.14 45 55.7 0.14 46 56.0 0.14 47 56.4 0.14 48 56.7 0.14 49 57.1 0.14 50 57.4 0.14 51 57.8 0.14 52 58.1 0.14	40	53.8	0.14
43 55.0 0.14 44 55.3 0.14 45 55.7 0.14 46 56.0 0.14 47 56.4 0.14 48 56.7 0.14 49 57.1 0.14 50 57.4 0.14 51 57.8 0.14 52 58.1 0.14	41	54.2	0.14
44 55.3 0.14 45 55.7 0.14 46 56.0 0.14 47 56.4 0.14 48 56.7 0.14 49 57.1 0.14 50 57.4 0.14 51 57.8 0.14 52 58.1 0.14	42	54.6	0.14
45 55.7 0.14 46 56.0 0.14 47 56.4 0.14 48 56.7 0.14 49 57.1 0.14 50 57.4 0.14 51 57.8 0.14 52 58.1 0.14	43	55.0	0.14
46 56.0 0.14 47 56.4 0.14 48 56.7 0.14 49 57.1 0.14 50 57.4 0.14 51 57.8 0.14 52 58.1 0.14	44	55.3	0.14
47 56.4 0.14 48 56.7 0.14 49 57.1 0.14 50 57.4 0.14 51 57.8 0.14 52 58.1 0.14	45	55.7	0.14
48 56.7 0.14 49 57.1 0.14 50 57.4 0.14 51 57.8 0.14 52 58.1 0.14	46	56.0	0.14
48 56.7 0.14 49 57.1 0.14 50 57.4 0.14 51 57.8 0.14 52 58.1 0.14	47	56.4	0.14
50 57.4 0.14 51 57.8 0.14 52 58.1 0.14	48		0.14
50 57.4 0.14 51 57.8 0.14 52 58.1 0.14	49	57.1	0.14
51 57.8 0.14 52 58.1 0.14	50		
52 58.1 0.14	51	57.8	
	52		0.14
1	53	58.5	0.14

54	58.8	0.13
55	59.1	0.13
56	59.5	0.14
57	59.8	0.14
58	60.1	0.14
59	60.5	0.14
60	60.8	0.14
61	61.1	0.14
62	61.5	0.14
63	61.8	0.14
64	62.2	0.14
65	62.5	0.14
66	62.9	0.14
67	63.2	0.14
68	63.5	0.14
69	63.9	0.14
70	64.3	0.14
71	64.6	0.14
72	65.0	0.14
73	65.3	0.14
74	65.7	0.14
75	66.0	0.14
76	66.4	0.14
77	66.8	0.14
78	67.2	0.14
79	67.5	0.14
80	67.9	0.14
81	68.3	0.14
82	68.7	0.14
83	69.1	0.14
84	69.6	0.15
85	70.0	0.15
86	70.5	0.15
87	70.9	0.15
88	71.4	0.16
89	71.9	0.16
90	72.5	0.17
91	73.0	0.17
92	73.7	0.18

93	74.3	0.19
94	75.1	0.20
95	76.0	0.22
96	76.9	0.24
97	78.1	0.26
98	79.5	0.29
99	81.2	0.33
100	83.7	0.39

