3.5.2 Efficacy Endpoints

Primary Efficacy Endpoints

- 1. The change in VAS score at 3 months compared to baseline (pilot phase)
- 2. The change in VAS score at 12 months compared to baseline (comparative phase)

Secondary Efficacy Endpoints

- 1. The change in VAS score at 1, 3, 6, 9 and 12 months compared to baseline
- 2. The change in PROMIS® score at 1, 3, 6, 9 and 12 months compared to baseline
- 3. The change in FHSQ score at 1, 3, 6, 9 and 12 months compared to baseline
- 4. Changes in pain medication use at 1, 3, 6, 9 and 12 months compared to baseline
- 5. Rate of recurrence of symptomatic neuroma within 12 months

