For subjects who have not completed the study, who cannot be contacted, and who do not have a known reason for discontinuation (e.g., withdrew consent or adverse event, etc.), the reason for discontinuation will be "lost to follow-up".

Subject Non-Compliance

A subject is considered noncompliant if they fail to return for follow-up.

The Visual Analog or Analogue Scale for Pain

This pain scale is designed to present to the respondent a rating scale with minimum constraints. Respondents will mark the location on the 100-millimeter line corresponding to the amount of pain they experienced. VAS data are recorded as the number of millimeters from the left of the line with the range 0-100.

Patient Reported Outcome Measurement Information System Questionnaires

The PROMIS questionnaire is a set of person-centered measures that evaluates and monitors physical, mental, and social health in adults and children. Measures are applicable to the general

population and to those with chronic conditions. For this study, PROMIS measures will be used to monitor a subject's physical health/pain. The following six scales will be measured¹:

- Physical function
- Pain intensity
- Pain interference
- Fatigue
- Sleep disturbance
- Pain behavior

For each scale, raw scores are calculated by summing each individual question score. Raw scores are converted to a standard score with a mean of 50 and standard deviation of 10. The score is not valid if any items are missing. Conversion tables are listed in Appendix B.

Foot Health Status Questionnaire

The FHSQ was developed to help better measure responsiveness in overall foot health status. Four scales will be measured²:

- Foot Function
- General Foot Health
- Footwear
- Foot Pain

Each scale has a score ranging from 0 to 100, with higher scores representing better foot health and quality of life. When fewer than 50% of responses for any one scale are missing, any missing values for that scale are assigned to the average value of the non-missing questions.

Scoring will be calculated by transforming the raw scores for each sub-domain into an easily interpretable 0-100 scale, with 0 indicating poorest foot health and 100 representing no problems. The following formula was used to convert the raw scores for each sub-domain:

$$X = \left(\frac{X_{raw} - X_{worst}}{X_{optimal} - X_{worst}}\right) \times S_{optimal}$$

where,

 X_{raw} = Total score of the sub-domain

 X_{worst} = Score of the poorest state of foot health

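### SAP Appendix B gives PROMIS Pain Interference raw scores 18 and 19 the same T-score (58.1); row 18 looks about 0.7–0.8 points too high and should be verified

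*SAP*

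**What the plan says.** SAP section 6 (definition of the PROMIS questionnaires) lists six scales to be measured, Pain Interference among them. Item scores are summed, and then: "Raw scores are converted to a standard score with a mean of 50 and standard deviation of 10". The rule for doing so is a lookup: "Conversion tables are listed in Appendix B".

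SAP section 14, "Appendix B: PROMIS Questionnaire Scoring Conversion Tables", holds one table per scale. The Pain Interference rows at issue are:

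| Raw sum | T-score | SE |
|---|---|---|
| 17 | 56.6 | 1.4 |
| 18 | 58.1 | 1.3 |
| 19 | 58.1 | 1.3 |
| 20 | 58.8 | 1.3 |

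Two other places bear on how far this reaches. Protocol 3.5.2 has a secondary efficacy endpoint that names no scale: "The change in PROMIS® score at 1, 3, 6, 9 and 12 months compared to baseline". The secondary list in SAP 9.2.1 has a single PROMIS entry, at Month 12, and it concerns a different scale: "The change from baseline of PROMIS Pain Behavior".

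**The concern.** A conversion from summed score to T-score should rise with every added raw point, and this one does in every other row. A flat step straight after a step of double size is the pattern left when one row's value is typed into the row above it.

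Appendix B is the scoring rule, so a programmer who follows the SAP would code 58.1 for raw 18. Each such score would then be slightly too high, a real one-point move between 18 and 19 would vanish, and a move between 17 and 18 would be about doubled. Because the analysis is of change from baseline, the error can enter at baseline or at follow-up, with opposite signs.

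**Working it through.** **Inputs.** The T-score columns of the six tables in SAP Appendix B; the Pain Interference standard errors from the same place; 86 randomized subjects at 1:1 (SAP 4), so 43 per arm. The documents give no formula for the conversion, so the table can be tested only against its own progression.

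**1. Ties in all six tables.** Rows: Physical Function 25, Pain Intensity 13, Pain Interference 33, Fatigue 33, Sleep Disturbance 33, Pain Behavior 81; total 218. The other five tables rise strictly, with smallest steps of 0.8, 2.4, 0.9, 1.0 and 0.3 in that order. The Pain Interference pair 18/19 is the only tie.

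**2. Steps around the tie.**

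| Step | Difference |
|---|---|
| 15 to 16 | 0.8 |
| 16 to 17 | 0.8 |
| 17 to 18 | 58.1 − 56.6 = 1.5 |
| 18 to 19 | 58.1 − 58.1 = 0.0 |
| 19 to 20 | 58.8 − 58.1 = 0.7 |
| 20 to 21 | 0.7 |

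Every other step from raw 12 to raw 37 lies between 0.6 and 0.9.

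**3. Which row is out of line?** Leave out both rows and interpolate linearly from raw 17 to raw 20:

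- raw 18: 56.6 + (58.8 − 56.6)/3 = 57.33, printed 58.1
- raw 19: 56.6 + 2 × (58.8 − 56.6)/3 = 58.07, printed 58.1

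A cubic fitted to raw 13 to 24 without these two rows gives 57.36 and 58.10. Both methods recover row 19 and miss row 18.

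As a cross-check, assume only one row is wrong:

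- Row 18 wrong: (56.6 + 58.1)/2 = 57.35. The steps from 17 to 20 become 0.75, 0.75 and 0.7, all inside the 0.6–0.9 range.
- Row 19 wrong: (58.1 + 58.8)/2 = 58.45. The steps become 1.5, 0.35 and 0.35, all outside it.

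**4. Size for one score.** 58.1 − 57.36 = 0.74 and 58.1 − 57.33 = 0.77, so about 0.7–0.8 T-points. Taking 0.75, this is 0.75/1.3 = 0.58 of the row's standard error and 0.075 of the reference SD of 10. It affects one of 33 possible raw scores.

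**5. Size for a group comparison.** Both arms use the same lookup, so the shift in the difference between arm means is 0.75 × (net difference between arms in the proportion at raw 18). For change scores, a subject contributes +0.75 if at raw 18 only at follow-up, −0.75 if only at baseline, and 0 if at both or neither.

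- One extra subject in one arm: 0.75/43 = 0.017 on that arm's mean.
- Assumed net imbalance of 5 percentage points: 0.75 × 0.05 = 0.04.
- Assumed net imbalance of 10 percentage points: 0.75 × 0.10 = 0.075.
- A shift of 0.1 would need 0.1/0.75 = 13 percentage points, or about 6 of 43 subjects.

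**The case against.** **No listed test uses the scale.** A reader might infer that a secondary endpoint test is compromised. The documents do not support that. The only PROMIS comparison in SAP 9.2.1 is Pain Behavior, which has its own table with no ties. SAP 9.4 on tertiary and exploratory efficacy shows no content in the public copy, so any use there cannot be judged. What remains is that Pain Interference is one of the six scales to be scored and that the protocol's PROMIS endpoint does not exclude it.

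**The correct value is unknown.** A reader might also go further and state as fact that every raw 18 is mis-scored, or enter 57.35. The documents contain no reference value; the evidence is the smoothness of the neighbouring rows. That evidence is strong on which row is suspect, but it does not supply the replacement.

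**It may be a transcription artefact.** Other parts of the appendix come out of the PDF badly, notably the Pain Behavior table. The Pain Interference rows are in sequence with all three columns aligned. Turning 57.3 or 57.4 into 58.1 would take two changed digits that land exactly on the next row's value. This is unlikely but not excluded, and checking the page settles it.

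**It is not a bias between arms.** The same table serves both groups, so the error matters to the comparison only through a chance or treatment-related imbalance at one raw score. This stands, and it is why the effect is so small.

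The Pain Behavior standard errors (0.13 to 0.53) may also catch the eye. No visible planned analysis uses that column, so nothing is asked about it here.

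**Conclusion.** The duplicate is in the current SAP, and the table's own progression points to row 18 as the wrong entry, with neighbouring rows implying about 57.3–57.4. Used as printed, the table would put raw 18 about 0.7–0.8 T-points too high and score a change between 18 and 19 as zero.

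The consequence is minor. Under an assumed imbalance of up to 10 percentage points at raw 18, the effect on a between-arm mean difference stays below 0.1 T-points, and no conclusion is likely to turn on it.

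The finding rests on two assumptions: that the published conversion rises smoothly through this range, as the rest of the table does, and that the printed page reads as transcribed. It is worth correcting because the table is the scoring rule and the repair is almost free.

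**What to change.** Check the Pain Interference raw 18 row in SAP Appendix B against the instrument's published conversion table and replace the T-score with the verified value; do not adopt the interpolated figure. Confirm that any scoring code already written uses the verified value, and rescore Pain Interference if it does not.

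The cost is one table cell and a short code check. No change to the design, the endpoints or the planned tests is needed.
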